8.3. Definition of an Adverse Event

An AE is any untoward medical occurrence in a clinical investigation patient administered a product or medical device; the event need not necessarily have a causal relationship with the treatment or usage. Examples of AEs include but are not limited to:

- Abnormal test findings;
- Clinically significant symptoms and signs;
- Changes in physical examination findings;
- Hypersensitivity;
- Drug abuse;
- Drug dependency.

Additionally, they may include the signs or symptoms resulting from:

- Drug overdose;
- Drug withdrawal;
- Drug misuse;
- Drug interactions;
- Extravasations;
- Exposure during pregnancy (EDP);
- Exposure via breastfeeding;

- Medication error;
- Occupational exposure;
- Worsening of signs and symptoms of the malignancy under study should be reported as AEs in the appropriate section of the CRF. Disease progression assessed by measurement of malignant lesions on radiographs or other methods should not be reported as AEs.

8.4. Medication Errors

Medication errors may result, in this study, from the administration or consumption of the wrong product, by the wrong patient, at the wrong time, or at the wrong dosage strength. Such medication errors occurring to a study participant are to be captured on the medication error CRF, which is a specific version of the AE page, and on the SAE form when appropriate. In the event of medication dosing error, the sponsor should be notified immediately.

Medication errors are reportable irrespective of the presence of an associated AE/SAE, including:

- Medication errors involving patient exposure to the investigational product;
- Potential medication errors or uses outside of what is foreseen in the protocol that do or do not involve the participating patient.

Whether or not the medication error is accompanied by an AE, as determined by the investigator, the medication error is captured on the medication error version of the AE page and, if applicable, any associated AEs are captured on an AE CRF page.

8.5. Abnormal Test Findings

The criteria for determining whether an abnormal objective test finding should be reported as an AE are as follows:

- Test result is associated with accompanying symptoms; and/or
- Test result requires additional diagnostic testing or medical/surgical intervention; and/or
- Test result leads to a change in study dosing (outside of protocol-stipulated dose adjustments) or discontinuation from the study, significant additional concomitant drug treatment, or other therapy; and/or
- Test result is considered to be an AE by the investigator or sponsor.

Merely repeating an abnormal test, in the absence of any of the above conditions, does not constitute an AE. Any abnormal test result that is determined to be an error does not require reporting as an AE.

8.6. Serious Adverse Events

An SAE is any untoward medical occurrence at any dose that:

- Results in death;
- Is life-threatening (immediate risk of death);
- Requires inpatient hospitalization or prolongation of existing hospitalization;
- Results in persistent or significant disability/incapacity (substantial disruption of the ability to conduct normal life functions);
- Results in congenital anomaly/birth defect;
- Progression of the malignancy under study (including signs and symptoms of progression) should not be reported as an SAE unless the outcome is fatal within the safety reporting period. Hospitalization due to signs and symptoms of disease progression should not be reported as an SAE. If the malignancy has a fatal outcome during the study or within the safety reporting period, then the event leading to death must be recorded as an AE and as an SAE with CTCAE Grade 5 (see the section on [Severity Assessment](#)).

Medical and scientific judgment is exercised in determining whether an event is an important medical event. An important medical event may not be immediately life-threatening and/or result in death or hospitalization. However, if it is determined that the event may jeopardize the patient or may require intervention to prevent one of the other AE outcomes, the important medical event should be reported as serious.

Examples of such events are intensive treatment in an emergency room or at home for allergic bronchospasm; blood dyscrasias or convulsions that do not result in hospitalization; or development of drug dependency or drug abuse.

8.6.1. Protocol-Specified Serious Adverse Events

There are no protocol-specified SAEs in this study. All SAEs will be reported by the investigator as described in previous sections and will be handled as SAEs in the safety database (see the section on [Serious Adverse Event Reporting Requirements](#)).

8.6.2. Potential Cases of Drug-Induced Liver Injury

Abnormal values of AST and/or ALT levels concurrent with abnormal elevations in total bilirubin level that meet the criteria outlined below in the absence of other causes of liver

injury are considered potential cases of drug-induced liver injury (potential Hy's law cases) and should always be considered important medical events.

The threshold of laboratory abnormalities for a potential case of drug-induced liver injury depends on the patient's individual baseline values and underlying conditions. Patients who present with the following laboratory abnormalities should be evaluated further to definitively determine the etiology of the abnormal laboratory values:

- Patients with AST or ALT and total bilirubin baseline values within the normal range who subsequently present with AST or ALT values $\geq 3 \times \text{ULN}$ concurrent with a total bilirubin value $\geq 2 \times \text{ULN}$ with no evidence of hemolysis and an alkaline phosphatase value $\leq 2 \times \text{ULN}$ or not available.
- For patients with pre-existing ALT **OR** AST **OR** total bilirubin values above the ULN, the following threshold values should be used in the definition mentioned above:
 - For patients with pre-existing AST or ALT baseline values above the normal range, AST or ALT value ≥ 2 times the baseline values and $\geq 3 \times \text{ULN}$, or $\geq 8 \times \text{ULN}$ (whichever is smaller).

Concurrent with:

- For patients with pre-existing values of total bilirubin above the normal range: Total bilirubin level increased from baseline by an amount of at least $1 \times \text{ULN}$ **or** if the value reaches $\geq 3 \times \text{ULN}$ (whichever is smaller).

The patient should return to the investigational site and be evaluated as soon as possible, preferably within 48 hours from awareness of the abnormal results. This evaluation should include laboratory tests, detailed history, and physical assessment. The possibility of hepatic neoplasia (primary or secondary) should be considered.

In addition to repeating measurements of AST and ALT, laboratory tests should include albumin, creatine kinase, total bilirubin, direct and indirect bilirubin, gamma-glutamyl transferase, PT/INR, and alkaline phosphatase. A detailed history, including relevant information, such as review of ethanol, acetaminophen, recreational drug, and supplement consumption, family history, occupational exposure, sexual history, travel history, history of contact with a jaundiced person, surgery, blood transfusion, history of liver or allergic disease, and work exposure, should be collected. Further testing for acute hepatitis A, B, or C infection and liver imaging (eg, biliary tract) may be warranted. All cases confirmed on repeat testing as meeting the laboratory criteria defined above, with no other cause for LFT abnormalities identified at the time, should be considered potential Hy's law cases irrespective of availability of all the results of the investigations performed to determine etiology of the abnormal LFTs. Such potential Hy's law cases should be reported as SAEs.

8.7. Hospitalization

Hospitalization is defined as any initial admission (even less than 24 hours) in a hospital or equivalent healthcare facility or any prolongation of an existing admission. Admission also includes transfer within the hospital to an acute/intensive care unit (eg, from the psychiatric wing to a medical floor, medical floor to a coronary care unit, or neurological floor to a tuberculosis unit). An emergency room visit does not necessarily constitute a hospitalization; however, the event leading to the emergency room visit should be assessed for medical importance.

Hospitalization does not include the following:

- Rehabilitation facilities;
- Hospice facilities;
- Respite care (eg, caregiver relief);
- Skilled nursing facilities;
- Nursing homes;
- Same-day surgeries (as outpatient/same day/ambulatory procedures).

Hospitalization or prolongation of hospitalization in the absence of a precipitating, clinical AE is not in itself an SAE. Examples include:

- Admission for treatment of a pre-existing condition not associated with the development of a new AE or with a worsening of the pre-existing condition (eg, for workup of persistent pre-treatment laboratory abnormality);
- Social admission (eg, patient has no place to sleep);
- Administrative admission (eg, for yearly physical examination);
- Protocol-specified admission during a study (eg, for a procedure required by the study protocol);
- Optional admission not associated with a precipitating clinical AE (eg, for elective cosmetic surgery);
- Hospitalization for observation without a medical AE;
- Preplanned treatments or surgical procedures. These should be noted in the baseline documentation for the entire protocol and/or for the individual patient;
- Admission exclusively for the administration of blood products.

Diagnostic and therapeutic noninvasive and invasive procedures, such as surgery, should not be reported as AEs. However, the medical condition for which the procedure was performed should be reported if it meets the definition of an AE. For example, an acute appendicitis that begins during the AE reporting period should be reported as the AE, and the resulting appendectomy should be recorded as treatment of the AE.

8.8. Severity Assessment

Adverse events will be assessed in accordance with NCI CTCAE version 4.03, see Table 6.

Table 6. CTCAE Criteria for Adverse Events

Grade	Clinical Description of Severity
0	No Change from normal or reference range (This grade is not included in the Version 4.03 CTCAE document but may be used in certain circumstances.)
1	MILD adverse event
2	MODERATE adverse event
3	SEVERE adverse event
4	LIFE-THREATENING consequences; urgent intervention indicated
5	DEATH RELATED TO adverse event

CTCAE = Common Terminology Criteria for Adverse Events

Note the distinction between the severity and the seriousness of an AE. A severe event is not necessarily an SAE. For example, a headache may be severe (interferes significantly with the patient's usual function) but would not be classified as serious unless it met one of the criteria for SAEs listed above.

8.9. Causality Assessment

The investigator's assessment of causality must be provided for all AEs (serious and non-serious); the investigator must record the causal relationship in the CRF, as appropriate, and report such an assessment in accordance with the SAE reporting requirements if applicable. An investigator's causality assessment is the determination of whether there exists a reasonable possibility that the investigational product caused or contributed to an AE; generally the facts (evidence) or arguments to suggest a causal relationship should be provided. If the investigator does not know whether or not the investigational product caused the event, then the event will be handled as "related to investigational product" for reporting purposes, as defined by the sponsor (see the section on [Reporting Requirements](#)). If the investigator's causality assessment is "unknown but not related to investigational product," this should be clearly documented on study records. In addition, if the investigator determines that an SAE is associated with study procedures, the investigator must record this causal relationship in the source documents and CRF, as appropriate, and report such an assessment in accordance with the SAE reporting requirements, if applicable.

8.10. Exposure During Pregnancy (EDP)

For both unapproved/unlicensed products and for marketed products, an exposure during pregnancy occurs if:

1. A female becomes, or is found to be, pregnant either while receiving or having been exposed (eg, because of treatment or environmental exposure) to the investigational product; or the female becomes or is found to be pregnant after discontinuing and/or being exposed to the investigational product;
 - An example of environmental exposure would be a case involving direct contact with a Pfizer product in a pregnant woman (eg, a nurse reports that she is pregnant and has been exposed to chemotherapeutic products).
2. A male has been exposed (eg, because of treatment or environmental exposure) to the investigational product prior to or around the time of conception and/or is exposed during his partner's pregnancy.

If a study patient or study patient's partner becomes or is found to be pregnant during the study patient's treatment with the investigational product, the investigator must submit this information to the Pfizer drug safety unit on an SAE report form and an EDP supplemental form, regardless of whether an SAE has occurred. In addition, the investigator must submit information regarding environmental exposure to a Pfizer product in a pregnant woman (eg, a patient reports that she is pregnant and has been exposed to a cytotoxic product by inhalation or spillage) using the EDP supplemental form. This must be done irrespective of whether an AE has occurred and within 24 hours of awareness of the exposure. The information submitted should include the anticipated date of delivery (see below for information related to termination of pregnancy).

Follow-up is conducted to obtain general information on the pregnancy and its outcome for all EDP reports with an unknown outcome. The investigator will follow the pregnancy until completion (or until pregnancy termination) and notify Pfizer of the outcome as a follow-up to the initial EDP supplemental form. In the case of a live birth, the structural integrity of the neonate can be assessed at the time of birth. In the event of a termination, the reason(s) for the termination should be specified and, if clinically possible, the structural integrity of the terminated fetus should be assessed by gross visual inspection (unless pre-procedure test findings are conclusive for a congenital anomaly and the findings are reported).

If the outcome of the pregnancy meets the criteria for an SAE (ie, ectopic pregnancy, spontaneous abortion, intrauterine fetal demise, neonatal death, or congenital anomaly [in a live-born baby, a terminated fetus, an intrauterine fetal demise, or a neonatal death]), the investigator should follow the procedures for reporting SAEs.

Additional information about pregnancy outcomes that are reported as SAEs follows:

- Spontaneous abortion includes miscarriage and missed abortion;
- Neonatal deaths that occur within 1 month of birth should be reported, without regard to causality, as SAEs. In addition, infant deaths after 1 month should be reported as SAEs when the investigator assesses the infant death as related or possibly related to exposure to the investigational product.

Additional information regarding the EDP may be requested by the investigator. Further follow-up of birth outcomes will be handled on a case-by-case basis (eg, follow-up on preterm infants to identify developmental delays). In the case of paternal exposure, the investigator will provide the study patient with the Pregnant Partner Release of Information Form to deliver to his partner. The investigator must document in the source documents that the patient was given the Pregnant Partner Release of Information Form to provide to his partner.

8.11. Occupational Exposure

An occupational exposure occurs when, during the performance of job duties, a person (whether a healthcare professional or otherwise) gets in unplanned direct contact with the product, which may or may not lead to the occurrence of an AE.

An occupational exposure is reported to the drug safety unit within 24 hours of the investigator's awareness, using the SAE report form, regardless of whether there is an associated AE/SAE. Since the information does not pertain to a patient enrolled in the study, the information is not reported on a CRF; however, a copy of the completed SAE report form is maintained in the investigator site file.

8.12. Withdrawal Due to Adverse Events (See Also the [Section 6.6 Patient Withdrawal](#))

Withdrawal due to AEs should be distinguished from withdrawal due to other causes, according to the definition of AE noted earlier, and recorded on the appropriate AE CRF page.

When a patient withdraws because of an SAE, the SAE must be reported in accordance with the reporting requirements defined below.

8.13. Eliciting Adverse Event Information

The investigator is to report all directly observed AEs and all AEs spontaneously reported by the study patient. In addition, each study patient will be questioned about AEs.

8.14. Reporting Requirements

Each AE is to be assessed to determine if it meets the criteria for SAEs. If an SAE occurs, expedited reporting will follow local and international regulations, as appropriate.

8.14.1. Serious Adverse Event Reporting Requirements

If an SAE occurs, Pfizer is to be notified within 24 hours of investigator awareness of the event. In particular, if the SAE is fatal or life-threatening, notification to Pfizer must be made immediately, irrespective of the extent of available AE information. This time frame also applies to additional new information (follow-up) on previously forwarded SAE reports as well as to the initial and follow-up reporting of EDP, exposure via breastfeeding, and occupational exposure cases.

In the rare event that the investigator does not become aware of the occurrence of an SAE immediately (eg, if an outpatient study patient initially seeks treatment elsewhere), the investigator is to report the event within 24 hours after learning of it and document the time of his or her first awareness of the AE.

For all SAEs, the investigator is obligated to pursue and provide information to Pfizer in accordance with the time frames for reporting specified above. In addition, an investigator may be requested by Pfizer to obtain specific additional follow-up information in an expedited fashion. This information collected for SAEs is more detailed than that captured on the AE CRF. In general, this will include a description of the AE in sufficient detail to allow for a complete medical assessment of the case and independent determination of possible causality. Information on other possible causes of the event, such as concomitant medications, vaccines, and/or illnesses, must be provided. In the case of a patient death, a summary of available autopsy findings must be submitted as soon as possible to Pfizer or its designated representative.

8.14.2. Non-Serious Adverse Event Reporting Requirements

All AEs will be reported on the AE page(s) of the CRF. It should be noted that the form for collection of SAE information is not the same as the AE CRF. Where the same data are collected, the forms must be completed in a consistent manner. For example, the same AE term should be used on both forms. AEs should be reported using concise medical terminology on the CRFs as well as on the form for collection of SAE information.

8.14.3. Medical Device Complaint Reporting Requirements

Not applicable.

8.14.4. Sponsor's Reporting Requirements to Regulatory Authorities

AE reporting, including suspected unexpected serious adverse reactions, will be carried out in accordance with applicable local regulations.

9. DATA ANALYSIS/STATISTICAL METHODS

Detailed methodology for summary and statistical analyses of the data collected in this study will be documented in a statistical analysis plan (SAP), which will be maintained by the sponsor. This document may modify the plans outlined in the protocol; however, any major modifications of the primary endpoint definition and/or its analysis will also be reflected in a protocol amendment.

9.1. Analysis Sets

9.1.1. Safety Analysis Set

The safety analysis set includes all enrolled patients who receive at least one dose of study treatment.

9.1.2. Full Analysis Set

The full analysis set includes all enrolled patients.

9.1.3. Per-protocol Analysis Set (evaluable for MTD)

The per protocol analysis set includes all enrolled patients who received at least one dose of study treatment and who did not have major treatment deviations during the Cycle 1. For the IV administration of PF-06801591, patients with major treatment deviations in the 21-day DLT observation period are not evaluable for the MTD assessment and will be replaced as needed to permit MTD estimation.

For the SC administration of PF-06801591, patients with major treatment deviations in the 28-day observation period will not be evaluable for DLT.

Major treatment deviations include:

- Administration of <50% of the planned dose of PF-06801591, provided that the reduction is not due to toxicity attributable to PF-06801591.
- Administration of >150% of the planned dose of PF-06801591.

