3.1.4. Criteria for Dose Finding

Maximum Tolerated Dose Selection for IV Administration

An mTPI method,⁷ targeting a DLT rate of 27.5% and an acceptable DLT interval (22.5% to 32.5%), will be utilized in the Part 1A dose escalation phase. The IV dose levels to be evaluated for the MTD following IV administration are listed in Table 2. If a high DLT rate is observed at the starting dose, the study may explore a lower dose than the starting dose or be stopped. Cohorts of 2 to 4 patients (Part 1A) will be enrolled at each selected dose level. The required number of patients per dose level will be managed according to Table 3.

Table 2. Table of Pre-Specified PF-06801591 IV Dose Levels

Dose Level	Dose (mg/kg)
1	0.5
2	1.0
3	3.0
4	10

The mTPI method relies upon a statistical probability algorithm, calculated using all patients treated in the current dose level to determine one of the following dose-finding decisions: the subsequent dose should be escalated, maintained at the current dose, or de-escalated in the next cohort of 2 to 4 patients (Part 1A), or the trial should be terminated (Table 3).

In principle, all patients must be evaluated for a minimum period of 21 days. If a patient withdraws from the study before Day 21 for reasons other than drug-related toxicity, another patient may be enrolled to replace that patient in the current cohort. However, if a patient discontinues close to Day 21 for reasons other than toxicity and due to an evident non drug-related event, the patient may be deemed evaluable for safety if safety assessments have been unremarkable and the investigator and sponsor's medical monitor both agree that the patient is evaluable for DLT safety observation.

1. The dose escalation Part 1 of the study will stop if any of the following criteria is met:
2. The maximum sample size has been achieved (approximately 40 patients in total);
3. 6 to 15 patients have been enrolled at a dose level that is predicted to be the MTD per the mTPI method; All dose levels explored appear to be overly toxic, and the MTD cannot be determined;
4. All pre-specified dose levels have been tested and all doses were deemed tolerable.

Table 3. Decision Rules for IV Administration

Number of Patients having DLT	Number of Patients Treated at a Dose Level													
	n=2	n=3	n=4	n=5	n=6	n=7	n=8	n=9	n=10	n=11	n=12	n=13	n=14	n=15
0	E	E	E	E	E	E	E	E	E	E	E	E	E	E
1	S	S	S	E	E	E	E	E	E	E	E	E	E	E
2	U	D	S	S	S	S	S	S	S	E	E	E	E	E
3		U	U	D	D	S	S	S	S	S	S	S	S	S

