3.1.5. Dose-limiting Toxicity Definition

Previous anti-PD-1 mAbs were administered in >1000 patients and were associated in the clinic with inflammatory adverse reactions resulting from increased or excessive immune activity (immune-mediated adverse reactions), likely to be related to the mechanism of action. Immune-mediated adverse reactions, which can be severe, may involve the gastrointestinal, skin, liver, endocrine, respiratory, renal, or other organ systems.¹²

Severity of AEs will be graded according to CTCAE version 4.03. For the purpose of a dose finding decision, any of the following drug-related AEs occurring during the first cycle of treatment (21 days for IV, or 28 days for SC) will be classified as DLTs following review by the investigators and the sponsor:

- **Grade 5 AE**
- **Hematologic toxicity:**
 - Any Grade 4 hematologic AE, with the following clarifications:
 - Grade 4 neutropenia lasting >5 days from initiation of granulocyte-colony stimulating factor.

- Grade 4 thrombocytopenia with bleeding.
- Platelet transfusion requirement or a platelet count <10,000/uL.
- **Non-Hematologic Toxicity**
 - Grade 4 non-hematologic AE;
 - Grade 3 AE lasting >7 days despite optimal supportive care (see [Appendix 8](#));
 - Grade 3 central nervous system AE regardless of duration;
 - Meets criteria for drug-induced liver injury ([Section 8.6.2](#)).

The following AEs will not be adjudicated as DLTs:

- Any Grade 3 endocrinopathy that is adequately controlled by hormonal replacement.
- Grade 3 AE of tumor flare (defined as local pain, irritation, or rash localized at sites of known or suspected tumor).
- Isolated Grade 3-4 laboratory abnormalities that are not associated with clinical sequelae and are corrected with supplementation/appropriate management within 72 hours of their onset.
- Grade ≥ 3 infusion reactions and allergic reactions will not be considered dose limiting as they are unlikely to be dose related, but all available information on these events will be collected. If Grade ≥ 3 infusion reactions occur in ≥ 2 of the first 10 patients at any dose level, or if the occurrence is $\geq 5\%$ thereafter, a mandatory pre-treatment regimen for all new patients will be implemented. The incidence of Grade 1 and 2 reactions will also be taken into account. If a total rate of >10% all-grade infusion or allergic reactions is observed, a mandatory pre-treatment regimen for all new patients will be implemented.

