- Patients should be pretreated with acetaminophen and diphenhydramine (or other antihistamine) approximately 0.5 to 2 hours before each PF-06801591 administration. Pretreatment medications will not be supplied by Pfizer. Suggested starting doses are 650 to 1000 mg acetaminophen and 50 mg diphenhydramine (or equivalent of other antihistamine) IV or oral. Two (2) additional doses of acetaminophen may be administered approximately every 4-6 hours after the initial pretreatment or as needed.

Hypersensitivity reactions:

In the case of a hypersensitivity reaction, the patient will be treated symptomatically, with supportive care and further monitoring until the end of the study. Study infusions may be stopped.

Guidelines for the management of hypersensitivity reactions are as follows:

1. NCI-CTCAE Grade 1 allergic reaction or cytokine release syndrome:
 - a. Monitor for worsening condition. If the reaction worsens, stop the infusion. Use premedication for subsequent infusions, as described above.
2. NCI-CTCAE Grade 2 allergic reaction or cytokine release syndrome:
 - a. Stop PF-06801591 infusion.
 - b. Administer bronchodilators, oxygen, acetaminophen, etc. as medically indicated.
 - c. Resume infusion at 50% of previous rate once reaction has decreased to \leq Grade 1 in severity. Monitor closely for any worsening. If the reaction recurs, stop infusion. Institute premedication for subsequent infusions as described above.
3. NCI-CTCAE Grade 3 or Grade 4 allergic reaction or cytokine release syndrome or anaphylaxis:
 - Grade 3 anaphylaxis (hypersensitivity reaction) consists of symptomatic bronchospasm requiring parenteral medications with or without urticaria, allergy-related edema/angioedema, or hypotension.
 - Grade 4 anaphylaxis (hypersensitivity reaction) is a life-threatening event requiring urgent intervention.
 - a. Stop the PF-06801591 infusion immediately and disconnect infusion tubing from the patient.
 - b. Administer epinephrine, bronchodilators, antihistamines, glucocorticoids, intravenous fluids, vasopressor agents, oxygen, etc. as medically indicated.
 - c. Telephone sponsor or designated representative to report an SAE as per [Section 8.6](#).
 - d. For a NCI-CTCAE Grade 3 or 4 hypersensitivity reaction, discontinue study treatment.
4. Re-treatment following Grade 1 or Grade 2 allergic reactions or cytokine release syndrome:

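### A Part 1 patient under-dosed by an infusion or allergic reaction stays evaluable for MTD although the reaction cannot be a DLT, so a barely exposed patient counts as DLT-free in Table 3

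*Protocol*

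**What the plan says.** Protocol 9.1.3 defines the set evaluable for MTD. One of its two listed major treatment deviations is "Administration of <50% of the planned dose of PF-06801591, provided that the reduction is not due to toxicity attributable to PF-06801591", and SAP 4.3 repeats it. The consequence for IV dosing is that "patients with major treatment deviations in the 21-day DLT observation period are not evaluable for the MTD assessment and will be replaced as needed"; for SC dosing, such patients are not evaluable for DLT.

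Protocol 3.1.5, repeated in SAP 9.1, lists events that will not be adjudicated as DLTs. From Grade 3 upwards, with no upper limit given, "infusion reactions and allergic reactions will not be considered dose limiting as they are unlikely to be dose related". The same section names a drug-related Grade 5 AE as a DLT.

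Protocol Appendix 7 tells the site what to do in a Grade 3 or 4 reaction: "Stop the PF-06801591 infusion immediately and disconnect infusion tubing from the patient", and then "For a NCI-CTCAE Grade 3 or 4 hypersensitivity reaction, discontinue study treatment". After a Grade 2 reaction the infusion may resume at half rate, but "If the reaction recurs, stop infusion".

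On replacement, protocol 3.1.4 says: "If a patient withdraws from the study before Day 21 for reasons other than drug-related toxicity, another patient may be enrolled to replace that patient". It also bases the mTPI decision on everyone treated at the current level. SAP 2.2.1 repeats both points and adds the 28-day window for SC. SAP 6.2.1 summarises DLTs on the Per Protocol set.

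**The concern.** The exception in 9.1.3 is sensible when the toxicity that cut the dose short can itself be scored as a DLT, because dropping that patient would lose a bad outcome. For infusion and allergic reactions this reasoning fails. The event is attributable to the drug, so the patient is kept; it is barred from being a DLT, so the patient scores zero. Someone who received a small part of the dose is then counted as having tolerated it.

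This is a problem of exposure, not of follow-up. It arises even if the patient is observed for the full 21 or 28 days. DLT is the primary endpoint of Part 1 and the Part 1A cohorts hold 2 to 4 patients, so one patient can change a decision.

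**Working it through.** **1. The path, rule by rule.** Take an IV patient with a Grade 3 allergic reaction early in the first infusion.

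- Appendix 7: the infusion stops and treatment ends, so the dose can fall below 50% with no re-exposure.
- 9.1.3 and SAP 4.3: the shortfall is due to attributable toxicity, so there is no major deviation and the patient is evaluable.
- 3.1.5 and SAP 9.1: the reaction is not a DLT.
- 3.1.4: replacement is provided for withdrawal for reasons other than drug-related toxicity, which does not describe this patient.
- Table 3: n rises by one and the DLT count does not.

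**2. The plan's own figures.** Protocol 9.2.1 assumes escalation on 0/3 or 1/6. With true DLT rate p,

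P(escalate) = (1−p)³ + 3p(1−p)² × (1−p)³.

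At p = 0.3 this is 0.343 + 0.151 = 0.494; at p = 0.4 it is 0.216 + 0.093 = 0.309. All nine tabulated values reproduce (0.91 down to 0.001). Rebuilding Table 3 from the stated Beta(0.5, 0.5) prior, the 22.5% to 32.5% interval and the 0.95 threshold matches 88 of 97 cells. Eight of the other nine are the conservative overrides marked in Appendix 2; the ninth is 7/15. No Escalate cell is affected.

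**3. One barely exposed patient among the first three.** Give that patient DLT probability 0 but keep the patient in n:

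P(escalate) = (1−p)² + 2p(1−p) × (1−p)³.

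| True DLT rate | As stated | One such patient |
|---|---|---|
| 20% | 0.71 | 0.80 |
| 30% | 0.49 | 0.63 |
| 40% | 0.31 | 0.46 |
| 50% | 0.17 | 0.31 |

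This is an upper bound, because the patient could still have a different qualifying event.

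**4. Averaging over how often it happens.** The documents give no rate of dose-stopping reactions, so I assume q = 5%, 10% and 20% per patient and replace p by p(1−q) in the formula of step 2. At p = 0.4 the effective rates are 0.38, 0.36 and 0.32, and the escalation probabilities are 0.34, 0.38 and 0.45, against 0.31. Zero DLT probability for reactors is again assumed.

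**5. Effect in Table 3.** Adding one DLT-free patient at the same DLT count moves 1/4 Stay to 1/5 Escalate, 2/10 Stay to 2/11 Escalate, 2/3 De-escalate to 2/4 Stay, 3/6 De-escalate to 3/7 Stay, 2/2 Unacceptable to 2/3 De-escalate, and 3/4 Unacceptable to 3/5 De-escalate. No cell moves towards caution.

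**6. A fatal reaction.** In 3.1.5 a drug-related fatal allergic reaction meets both the Grade 5 DLT line and the open-ended Grade 3 or higher exclusion. Counted as a DLT, Table 3 gives Stay at 1/2, 1/3 and 1/4. Not counted, it gives Escalate at 0/2, 0/3 and 0/4.

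**The case against.** The strongest reply is that Table 3 is not applied mechanically. Protocol 3.1.1 doses one patient at each level and waits 48 hours; a second is enrolled only if no safety concern arises. A stopped infusion falls inside that window. DLTs are classified after review by investigators and sponsor, and 9.8 provides ongoing discussion of whether to keep enrolling. The list of major deviations in 9.1.3 is open-ended, and 3.1.4 does not forbid other replacements. Further Part 1B patients and late immune-related DLTs can correct an early decision.

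Part of this stands. The stagger mitigates the problem, but only when the first patient at a level is the one who reacts. Review and open wording leave room for judgement, but neither is a rule that takes this patient out of the count.

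A reader might go further in four ways that the documents do not support.

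- *Escalation after 0/2 at a true rate of 40% rises from 0.36 to 0.60.* That is (1−p)² against 1−p. It presupposes a reactor already in a cohort of exactly two, with no chance of another DLT. Averaged over the assumed 5%, 10% and 20% rates, (1−0.4(1−q))² is 0.38, 0.41 and 0.46.
- *The protocol expects two such reactions in the first ten patients.* In 3.1.5 that count is a trigger for mandatory pre-treatment, not a planned rate.
- *An SC reactor supports escalation.* Appendix 7's stop instructions are worded for infusions, SC data do not enter IV decisions, and SC has no higher planned level. At most, such a patient would dilute the boundary for moving to 150 mg.
- *The Part 2 dose is therefore unsafe.* Protocol 3.1.2 and 3.1.8 base that choice on Part 1 safety, PK, pharmacodynamics and activity, with injection volume also cited in 3.1.2. They do not rest it on a Table 3 MTD.

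**Conclusion.** The gap is real and clearest for IV dosing in Part 1. Followed as written, the rules place a barely exposed patient in the denominator as DLT-free, and the bias runs only towards escalation or towards a diluted toxicity boundary.

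The upper bound is 0.49 to 0.63 at a true rate of 30% and 0.31 to 0.46 at 40%, given one such patient among the first three. The averaged shift at 40% is 3 to 14 points (0.34 to 0.45 against 0.31) over assumed reaction rates of 5% to 20%. These figures rest on the 0/3-or-1/6 rule and on no other DLT in the reactor. Grade 3 or 4 infusion or allergic reactions are the clear route. A Grade 2 reaction need not end in under-dosing, and cytokine release syndrome is not named in the exclusion.

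With the Part 2 dose already selected, the remaining effect is mainly on the reported DLT denominators and any MTD statement. The contradiction over a fatal reaction is separate. The documents do not say which line governs, and I do not infer it.

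**What to change.** In protocol 9.1.3 and SAP 4.3, change the end of the exception so that it applies only where the reduction is due to a DLT. A patient with less than 50% of the planned Cycle 1 dose and no DLT would then not be evaluable for MTD or DLT, would be left out of the Table 3 and Appendix 2 counts, would be replaced as needed, and would stay in the safety set. A patient under-dosed because of a DLT would still be counted.

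Align the replacement and denominator text in protocol 3.1.4 and SAP 2.2.1, which now counts all patients treated at the level. With such patients removed and replaced, the escalation probabilities stated in 9.2.1 hold again.

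Separately, reconcile the Grade 5 line with the infusion and allergic reaction exclusion in protocol 3.1.5 and SAP 9.1, so that a fatal reaction has one classification.

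The cost is a few phrases in each document and an occasional replacement patient, which 9.1.3 already accepts for other under-dosed IV patients.
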